8.4.7 Tumour Assessment

Tumour assessment is done at the treating site according to RECIST 1.1 (Eisenhauer et al. 2009; Appendix 1 - RECIST Criteria) and Immune-related response criteria ([Appendix 2](#) - Immune-related Response Criteria). MRI/CT (chest, abdomen and pelvis) slice thickness must be 5 mm or less. In case of suspicion of pseudoprogression and subjective stable disease (no clinical deterioration) a second tumour evaluation should be carried out at least 4 weeks after the first response evaluation even if the subject has been deemed to discontinue from the study. For evaluable subjects, the response will be reported in each cohort as the numbers of subjects who have CR, PR, SD, or progressive disease as well as irCR, irPR, irSD, or ir-progressive disease.

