8.10 Treatment beyond RECIST defined disease progression

In case of suspicion of pseudoprogression and subjective stable disease (no clinical deterioration), a second tumour evaluation should be carried out at least 4 weeks after the first response evaluation even if the subject has been deemed to discontinue from the study.

Subjects treated with FP-1305 may continue treatment beyond initial RECIST 1.1 defined progressive disease, assessed by the investigator, as long as they meet the following criteria (assessment of the criteria must be recorded in the source data):

- 1) Investigator-assessed clinical benefit
- 2) Tolerance of study treatment
- 3) Stable or improved ECOG performance status
- 4) Treatment beyond progression will not delay an imminent intervention to prevent serious complications of disease progression (e.g., central nervous system (CNS) metastases)

A follow-up scan should be performed after 4 weeks to determine whether there has been a decrease in the tumour size or continued progressive disease. The assessment of clinical benefit should be balanced by clinical judgment as to whether the participant is clinically deteriorating and unlikely to receive any benefit from continued treatment with FP-1305. If the investigator feels that the subject continues to receive clinical benefit by continuing treatment, the subject should remain on the trial and continue to receive monitoring. For the subjects who continue study therapy beyond progression, further progression is defined as an additional 10% increase in tumour burden with a minimum 5 mm absolute increase from the time of the initial progressive disease. This includes an increase in the sum of diameters of all target lesions and/or the diameters of new measurable lesions compared to the time of initial progressive disease. FP-1305 treatment should be discontinued permanently upon documentation of further progression.

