10.4 Trial Subject Withdrawal/Discontinuation

Administration of the IMP and the subject's participation in the study must be discontinued for any of the following reasons:

- 1) Withdrawal of informed consent
- 2) In the case of any clinical AE, laboratory abnormality or illness leading to the conclusion by the investigator that participation into the trial is not the best interest of the subject
- 3) In the occurrence of toxicities as defined in [Section 8.9](#)
- 4) Pregnancy
- 5) Termination of the trial by the Sponsor
- 6) Loss of ability to freely provide informed consent
- 7) Inability to comply with protocol
- 8) Disease progression (for treatment beyond RECIST defined disease progression see [Section 8.10](#))
- 9) Dosing delays greater than the maximum allowed dosing delays as defined in [Section 8.7](#)

All trial subjects should comply with the protocol specified follow-up procedures as outlined in [Section 8.5](#). The only exception to this requirement is a withdrawal of informed consent for all trial procedures or when a subject has lost the ability to consent freely. All data collected until the withdrawal of informed consent will be analysed and included into trial data.

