irPR	Decrease of $\geq 30\%$ in TMTB relative to baseline. Confirmation by two consecutive observations not less than 4 weeks apart is required.
irProgressive disease	Minimum 20% increase and minimum 5 mm absolute increase in TMTB compared to nadir. Confirmation by two consecutive observations not less than 4 weeks apart is required.
irSD	No irCR or irPR in the absence of irProgressive disease.

Notes:

1. To achieve "unequivocal progression" on the basis of the non-target disease, there must be an overall level of substantial worsening in non-target disease and symptoms such that, even in presence of irSD or irPR in target disease, the overall tumour burden has increased sufficiently to merit discontinuation of therapy.

B. Evaluation of Non-Target Lesions

Response Category	Description
irCR	Disappearance of all non-target lesions
irProgressive disease	Unequivocal progression of non-target lesions

C. Evaluation of Best Overall Response

The best overall response is the best response recorded from the start of treatment until disease progression. In general, the patient's best response assignment will depend on the achievement of both measurement and confirmation criteria.

D. Overall Responses for All Possible Combinations of Tumour Responses in Target and Non-Target Lesions with or without the Appearance of New Lesions

Target Lesions	Non-target Lesions	Overall Response
irCR	irCR	irCR
irCR	non-irProgressive disease	irPR
irPR	irCR	irPR
irPR	non-irProgressive disease	irPR
irSD	non-irProgressive disease	irSD
Any	irProgressive disease	irProgressive disease

Patients with a global deterioration of health status requiring discontinuation of treatment without objective evidence of disease progression at that time should be classified as having "symptomatic deterioration." Every effort should be made to document the objective disease progression, even after discontinuation of treatment.

Frequency of Tumour Re-evaluations

For the trial, clinical response rate, disease control rate (CR+PR+SD), PFS and duration of response will be evaluated by CT or MRI scan of the abdomen at baseline. Repeat imaging must be performed with the same method and will be performed according to schedule of assessment.

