12.1 Primary outcome variables

ORR (CR or PR), CBR (CR, PR or SD) and irORR (irCR or irPR) will be reported as the proportion of subjects of all efficacy evaluable subjects within each tumour type cohort and dosing regimen, both at cycle 4 and at cycle 7. The 90% confidence intervals for ORR, CBR and irORR will be calculated. Results from each tumour type (disease group) will be reported separately. There has been

recent debate about the definition of CBR and DCR. Recent article (“Clinical endpoints in oncology - a primer” by Delgado and Guddati) described that for CBR the SD should last at least 6 months. For clarity, and in order to comply with study protocol the tumour imaging results according the RECIST 1.1 will be presented by cycles (doing so there is no difference in the definition of DCR and CBR). Additionally, we are reporting the duration of SD to capture also that utility.

It should be noted that although the protocol states that irORR should be evaluated, it requires confirmation of irCR or irPR from an additional tumour evaluation carried out at least 4 weeks after irCR or irPR was established. However, due practical limitations in the population of subjects recruited for this study, the additional tumour evaluation could not be carried out on several occasions (only single PR result so far) and for this reason, ancillary information (e.g., no signs of clinical progression) will be reported for patients who continue treatment beyond PD.

When progression occurs, patients can continue treatment if IMP still is judged beneficial for the patient, i.e., clinical status does not indicate progression. This will be summarized using the following categories:

- No evidence of progression
- Evidence of progression, IMP still beneficial
- Evidence of progression, patient withdrawn

This presentation will be done for the first tumor imaging and first time of progression for the DCR subjects. Also, the confirmation image result will be reported for patients continuing IMP beyond progression.

Simon’s Two-Stage design will be used to evaluate efficacy and decide whether the cohort can be further expanded or not for Part III. The expansion of each disease group cohort is based on CBR (at cycle 4 or at cycle 7 for the Q3W dosing regimen) and the required proportion to proceed to Part III is 1/10. The same definition, CBR at cycle 4 or at cycle 7, will be used for the classification of subjects (DCR vs non-DCR) in the analyses.

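### A subject who meets the irPD threshold on tumour burden alone and stops without a later scan counts, read literally, as irSD

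*Protocol*

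**What the plan says.** **Reporting.** Protocol section 8.4.7 has tumours assessed by RECIST 1.1 and by the immune-related criteria. For evaluable subjects, each cohort is to be reported by RECIST class "as well as irCR, irPR, irSD, or ir-progressive disease".

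**Definitions (protocol Appendix 2).** On target lesions, irPD is "Minimum 20% increase and minimum 5 mm absolute increase in TMTB compared to nadir. Confirmation by two consecutive observations" at least 4 weeks apart. irSD is "No irCR or irPR in the absence of irProgressive disease". For non-target lesions, unequivocal progression is irPD with no confirmation stated, and it makes the overall response irPD whatever the target lesions show.

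**Repeat scans.** Section 8.4.7: "In case of suspicion of pseudoprogression and subjective stable disease (no clinical deterioration) a second tumour evaluation should be carried out". The interval is to be 4 weeks or more, and the request covers even a subject who is due to leave the study. Section 8.10 repeats this and, for subjects treated past RECIST progression, adds: "A follow-up scan should be performed after 4 weeks to determine whether there has been a decrease in the tumour size". Otherwise progression is a reason to discontinue (section 10.4), and the post-treatment assessments in section 8.5 list no tumour imaging.

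**SAP.** Section 12.1 of the Part II SAP defines irORR as irCR or irPR. On confirming those responses it concedes that "the additional tumour evaluation could not be carried out on several occasions". It has no corresponding rule for an irPD that was never confirmed. The protocol and the Part I SAP have none either.

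**The concern.** The condition for calling irPD on TMTB is a second observation, but the plan does not arrange that observation for everyone who meets the threshold. Someone whose tumour burden has clearly grown, in whom pseudoprogression is not suspected or who has deteriorated, and who stops, falls outside both triggers for a repeat scan. Because irSD is defined by what is absent, an unconfirmed irPD lands there by default.

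Any resulting error has a known direction: progression is relabelled as stability, never the reverse. In uncontrolled cohorts of about ten, an excess of irSD over RECIST SD is what a reader of an immunotherapy trial might take for pseudoprogression or delayed benefit. Without a rule, the statistician must either follow the residual definition or choose a class after seeing the data.

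**Working it through.** The plan states no figure on this point, so the check is to follow one subject through the rules and then see how the counts respond.

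**Tracing the rules.** Take a subject with a baseline scan and a Cycle 4 scan. TMTB is at least 20% and at least 5 mm above nadir, there is no unequivocal non-target progression, and the subject stops.

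1. *Must the subject be classed?* Yes. A baseline scan and one on-treatment scan put the subject in the efficacy evaluable population (protocol 15.1; Part II SAP section 8), and 8.4.7 reports evaluable subjects.
2. *Is a second scan requested?* Not if pseudoprogression is not suspected or the subject has deteriorated (8.4.7, 8.10), and treatment has not continued past progression (8.10). Section 8.5 schedules none.
3. *Target-lesion class under Appendix 2?* Not irCR or irPR. Not irPD, because confirmation is missing. The remaining class is irSD.
4. *Overall class?* In the Appendix 2 combination table, target irSD with no non-target progression gives irSD.
5. *Is there another class?* The RECIST table in Appendix 1 has a not-evaluable row; the Appendix 2 table does not. The symptomatic-deterioration paragraph covers only subjects without objective evidence of progression, so it does not apply.

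Two limits follow from the same text. New measurable lesions are added to TMTB, so progression through them also needs confirmation; but a new lesion that leaves TMTB below the threshold is correctly irSD by design. And if the table shows best response, the affected subjects are those who meet the threshold at their first on-treatment scan, because a subject who was stable earlier keeps irSD legitimately.

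**Effect on the counts (illustration; every input is assumed).** Cohort of 10: no immune-related responders, 2 subjects below the irPD threshold, 8 progressors who stop with no second scan. Let t be the number of the 8 who progressed on TMTB alone. Then irSD = 2 + t, irPD = 8 − t, and irORR = 0/10.

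| t | irSD | irPD | irORR |
|---|---|---|---|
| 0 | 2 | 8 | 0/10 |
| 4 | 6 | 4 | 0/10 |
| 6 | 8 | 2 | 0/10 |
| 8 | 10 | 0 | 0/10 |

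The shift equals t. It is zero when every such progressor also has unequivocal non-target progression.

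**What uses these counts.** irORR counts irCR and irPR only, and irSD and irPD are both non-responses. CBR and PFS are defined by RECIST 1.1. The Part III expansion rule (protocol 15.7; Part II SAP 12.1) uses CBR. None of them takes irSD or irPD as an input.

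**The case against.** The strongest reply is that these subjects are visible as progressors elsewhere. Section 8.4.7 reports RECIST classes beside the immune-related ones, so the same person appears there as PD. Section 12.1 of the Part II SAP also plans a three-way summary at the first tumour imaging, one category of which is subjects with evidence of progression who were withdrawn. This stands, and it limits the harm: nobody's progression disappears from the report. It does not settle the immune-related count, which would then disagree with the other displays for a reason that no one has written down.

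Second, no sentence instructs anyone to score an unconfirmed irPD as irSD. Appendix 2 says that best response generally depends on both measurement and confirmation, which could also be taken to mean unconfirmed or not evaluable. This stands too: irSD is the literal result of a residual definition and not a stated instruction. But Appendix 2 offers no other class.

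Third, the footnotes to the Part I and Part II assessment schedules say that other imaging done by the site will be collected, so some subjects who stop may have a later scan. That reduces the number affected; it does not class those who have none.

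Fourth, the SAP's remark about missed evaluations concerns confirmation of irCR and irPR. It is not evidence of how often irPD went unconfirmed.

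Finally, calling a single scan irPD would override Appendix 2's own confirmation requirement. That is a fair point against merging the two, and it is why the fix uses a separate column.

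**Conclusion.** The point holds in a limited form. The scan triggers do not supply the confirmation that Appendix 2 demands, and for a subject who meets the irPD threshold on TMTB alone and stops without a later scan, the written definitions give irSD. The effect is confined to the irSD and irPD counts and to anything built on them.

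A reader might go further and infer that most first-scan progressors will be tabulated as irSD, sizing this as an assumed progression rate times the share not re-scanned, for example 0.8 × 0.75 = 0.60. The documents do not support that. They give neither input, and the product has no term for non-target progression, which is irPD without confirmation. Immune-related disease control is also not an endpoint in the protocol or either SAP. A reader might likewise suspect that irORR or the decision to expand a cohort is biased; neither uses the affected classes.

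The size is therefore unknown and could be zero. The conclusion rests on reading the irSD definition literally. The repair is worth making because the direction of the error is known and correcting it is cheap.

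**What to change.** In protocol Appendix 2 and section 12.1 of the Part II SAP, state that:

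- irSD requires TMTB below the irPD threshold;
- a scan that meets the threshold and has no later evaluable scan is reported as unconfirmed irPD, in its own column, separate from confirmed irPD and never as irSD.

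This leaves the confirmation requirement for irPD as it is and changes no scan schedule or treatment rule. The cost is the wording and one table column, with no extra scans.

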8.5 Assessments during the Post-Treatment Period

The post-treatment period starts once the subject has completed the treatment period or stopped the treatment permanently (see [Section 10.4](#)). Once it has been decided that a subject will permanently stop treatment, a Follow-up Visit should be performed 4 weeks (+/- 1 week) after their last dose of IMP. If the last IMP dose was >5 weeks at the time of the decision, the Follow-up Visit should be performed as soon as possible. If the subject discontinued the treatment period due to AEs, the subject

must be followed up until the AEs have resolved or no change is the AE status is observed over the period.

- Vital signs (blood pressure, heart rate, body temperature and respiratory rate).
- A targeted physical examination covering the major body systems (e.g. general appearance, head [ear, nose and throat], cardiovascular, eyes, respiratory, abdomen, urogenital, musculoskeletal, neurological, lymph nodes and skin)
- ECG (in Part I and II)
- ECOG performance status
- ADA sampling
- Blood samples
 - CBC
 - CMP
 - LDH
 - LDL Cholesterol
 - AFP (HCC subjects)
 - CRP
 - CA-125 (OC subjects)
 - CA19-9 (PDAC, gallbladder cancer, cholangiocarcinoma, gastric adenocarcinoma subjects)
 - CEA (CRC, ER+ BC, gastric adenocarcinoma subjects)
 - CA-15-3 (ER+ BC subjects)
- Serum pregnancy test (women of child-bearing potential only)
- AE assessment. Photographs to document visible AEs should be considered.
- Concomitant medications and interventional procedures (including herbal products)

8.6 Sample Collection

8.6.1 Tumour Paraffin Blocks

Tumour biopsy samples will be collected according to the schedule shown in Table 1, Table 2 or [Table 3](#), and following the instructions in the Central Laboratory Services Manual. As indicated, tumour biopsy may be collected also if any new lesions are present. Biopsy from new lesions is recommended only if assessed feasible by the investigator considering the location of the lesions and condition of the subject. Tumour paraffin blocks or cut slides thereof with a notification that the sample contains tumour cells will be sent to the central laboratory for CLEVER-1 assessment by e.g. immunohistochemistry. Other biomarkers and gene expression may be analysed and genetic analysis may be conducted with appropriate methods.

The blocks collected prior to consent will be returned to the study site on request and latest after the trial has ended. The genetic analyses are optional for all subjects entering the trial and will involve a separate subject consent procedure. Consenting to genetic sampling is not a prerequisite to participating in the main trial. Tumour samples collected due other reasons (e.g. unscheduled biopsy or another informative sample for clinical reasons) may be analysed for scientific purpose when available.

8.6.2 Blood Samples

Blood samples will be collected at defined time points (see [Table 1](#), [Table 2](#) and [Table 3](#) as well as the Central Laboratory Services Manual) and for additional research and development related to FP-1305, cancer treatment and disease pathology. PBMCs will be isolated from the blood samples. These cells may also be used for the extraction of ribonucleic acid (RNA)/DNA i.e, genetic analyses may

be conducted from these samples. The genetic analyses are optional for all subjects entering the trial and will involve a separate subject consent procedure. The subjects that give genetic consent will also have blood collected for ctDNA samples and subsequent analysis. Consenting to genetic sampling is not a prerequisite to participating in the main trial. RNA/DNA samples will be destroyed at latest 10 years after completion of this trial. If the subject withdraws the consent, the sample will be destroyed without undue delay. The samples will be sent to the central laboratory and will be analysed in Europe and the US. Specific details about blood sample collection, preparation and storages are provided in the Laboratory Manual. In addition, blood samples will be collected for local analyses e.g. for safety monitoring purposes. Auto-antibodies against liver can be considered in immune-related AEs.

8.7 Dose Modifications, Infusion Delays, Missed Doses and Special Cases

IMP infusion will be prepared based on the subject's predose weight at each cycle (if not available, the most recent weight should be used). No visit specific dose adjustments are allowed for FP-1305, except for weight change adjustments. However, the maximum amount of FP-1305 in one IMP infusion is 10 g and cannot be exceeded irrespective of the weight-based dose. Guidance will be provided in the Pharmacy Manual to ensure calculated doses do not exceed this limit. If the IMP cannot be administered at the scheduled visit for any reason, the IMP must be administered as soon as possible, below here are instructions for Q3W schema. Instructions for Q2W and Q1W schemas are in Protocol Addendum.

- If the delay is 1 to 7 days, the procedures based on the current visit should be performed, and the subsequent visit will follow 21 days from the date of the infusion that occurred.
- If the delay is more than 7 days, the dose is considered missed, and the next per protocol visit should be brought forward and performed as soon as possible. Note, that the tumour images are still to be taken at every scheduled time point
 - (e.g. if there is an eight day delay for Cycle 4 Day 1, Cycle 4 IMP is considered a missed dose. The infusion given eight days after the original schedule in this case is Cycle 5 IMP dose and the related Cycle 5 procedures should be performed. In addition, tumour imaging of Cycle 4 should be done.) The subsequent visit will follow 21 days from the date of the infusion that just occurred.
 - Cycle 2 is an exception: every effort should be made to ensure that Cycle 2 is not delayed. In unavoidable delay, Cycle 2 IMP administration and the related Cycle 2 procedures should be performed as soon as possible.

Subjects that miss two consecutive scheduled doses (more than 49 days from the previous dose) will discontinue the treatment and enter the follow-up period unless specific consultation and agreement occurs between the investigator, the Medical Monitor and the Sponsor justify continued trial therapy. These decisions must be carefully documented.

Additionally, intra-subject dose change may occur to the recommended Part II/Part III dose after it has been determined. This decision must be carefully documented.

8.7.1 Treatment beyond One Year

In case that, as judged by the investigator, it would be beneficial to continue the treatment beyond one year, the protocol allows the treatment according to normal clinical practice, in order to allow the treatment continuation of the study subjects, provided that the clinical development and manufacturing of FP-1305 continues and it is not available via other routes. If the treatment is continued beyond one year, the following procedures/assessments will be done:

- FP-1305 infusion every three weeks
- Collection of weight, vital signs, physical examinations, ECOG, CBC, and CMP pre-dose for every infusion during the second year of treatment
- All available clinical routine images will be utilized. 18- (\pm 1 month) and 24- (\pm 1 month) month images from the first dose are mandatory to take if not routinely taken at these timepoints
- Collection of treatment related adverse events
- Collection of survival data (limited to 1 year from the last IMP dose if the treatment has been continued beyond one year)

